3.3 Early Withdrawal of Subjects

3.3.1 Criteria for removal from study

Insert subject withdrawal criteria (e.g., safety reasons, failure of subject to adhere to protocol requirements, subject consent withdrawal, disease progression, etc.).

1. Participant decides to withdraw from the parent-training program
2. Participant decides to withdraw at any point from the survey

Providers who decide to not deliver the module.

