7.2.3 Post-parenting Intervention Assessment

Provide a description as defined above and format accordingly.

Completion of the parenting intervention is specific to each parenting program. For PAT, completion of intervention (for the purposes of our research) is at the end of the fifth foundational visit. For Incredible Years, completion of intervention (for the purposes of our research) is the penultimate session – this is the last session in which content is delivered; the final session is a celebration and graduation. For SafeCare, completion of intervention (for the purposes of our research) is at the conclusion of the parenting module (6 weeks).

Parents will be provided with another paper survey. Those who have not agreed to participate in the research will be allowed to leave. Participants will complete the APQ and Module Assessment (‘Measure_ParentAssessmentTool’ in supporting documents).

7.2.4 One-week Post-parenting (control) OR Post-parenting and Module Assessment (Experimental group)

Provide a description as defined above and format accordingly.

One-week after completing the parenting program (7.2.3), parents in the control condition that have agreed to participate in the research will be contacted by the research team to complete the third assessment, the APQ, Module Assessment ('Measure_ParentAssessmentTool'). {This will happen within a normally scheduled session of PAT or SafeCare, and will require an additional visit for the IY participants}

The week after the conclusion of event 7.2.3, providers in the experimental condition deliver the Smart Parents – Safe and Healthy Kids module to their parents. The parent and provider will complete a short survey about the content of the session. This is done each time the module is delivered to measure fidelity. Additionally, provider-participants will record any two SPSHK sessions where the participating parent(s) agree to the recording. If the parent in the individual session—or any parent in the group session—declines to be audio recorded, the SPSHK module will be delivered as usual (including the fidelity survey), but the session will not be audio recorded.

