Immediately following delivery of the SPSHK module, those in the experimental group will complete the APQ, Module Assessment, and a questionnaire asking about their overall satisfaction with the module ('Measures_Parent Satisfaction Survey'). Parents will complete their fidelity assessment in addition to the Parent Satisfaction Survey ('SPSHK Parent Fidelity Monitoring') as part of their post-intervention assessment packet. As the parent fills out this form, the provider will complete the self-reported fidelity assessment ('SPSHK Provider Fidelity Monitoring_V2').

The audio recordings will be reviewed by the PSU study team using the 'SPSHK Research Fidelity Monitoring v2.1' form. The form assesses which aspects of the curriculum were delivered and to what degree (incomplete v. complete) to the family. These observations will be compared with provider self-report and parent report. Two visits will be recorded and scored for fidelity.

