7.2.5 One-month Follow-up Assessment

Provide a description as defined above and format accordingly.

One month after 7.2.4, when intervention is complete -- the post-parenting intervention assessment for the control group and the post-module assessment for the experimental group, a member of the research team will follow up with participants using the preferred method of contact they indicated in 7.2.1 and distribute the final survey packet over email (link to an electronic version of the survey) or a hard copy through the mail with a prepaid envelope for return to Penn State. They will complete the Module Assessment and APQ.

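### An experimental parent who completes T2 but does not receive the module has no T3 trigger and no T4 date, so post-module outcomes in that arm come only from recipients

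*Combined protocol and SAP*

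**What the plan says.** The labels T1 to T4 are those of the payment table in section 14.0.

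- **T2, both arms (7.2.3).** "Participants will complete the APQ and Module Assessment". The Module Assessment is the primary measure, and it is also given at T1.
- **T3, control (7.2.4).** "One-week after completing the parenting program (7.2.3), parents in the control condition that have agreed to participate in the research will be contacted". The contact comes from study staff. On setting: "This will happen within a normally scheduled session of PAT or SafeCare, and will require an additional visit for the IY participants".
- **T3, experimental (7.2.4).** "The week after the conclusion of event 7.2.3, providers in the experimental condition deliver the Smart Parents" module to their parents, and then: "Immediately following delivery of the SPSHK module, those in the experimental group will complete the APQ, Module Assessment, and a questionnaire" on satisfaction. The list of time points in 7.1 and the table in 14.0 also label this assessment as following the module.
- **T4 (7.2.5).** "One month after 7.2.4, when intervention is complete", which the text then explains as "the post-parenting intervention assessment for the control group and the post-module assessment for the experimental group".
- **Removal (3.3.1).** Parents are removed if they leave the programme or the survey. Missing the module is not listed. For providers, the criterion is "Providers who decide to not deliver the module". Nothing is said about the parents those providers serve.
- **Analysis (8.3).** No model, analysis population or missing-data rule is fixed.

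**The concern.** T3 and T4 are the only assessments that can show an effect of the module, because T1 and T2 precede it in both arms. In the experimental arm both are reached through delivery. A parent who misses the module session and is not given it later, or whose provider does not deliver it, may still be enrolled and reachable. The protocol does not say when, or how, to assess that parent.

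Receipt is settled after randomisation and depends on attendance and on provider willingness, both of which plausibly relate to the outcome. If staff follow the text, experimental outcomes come from recipients, while control outcomes are sought from every control who reached T2. Section 2.1 relies on randomisation to exclude systematic differences between the groups. It does not do so for this comparison, and answers not collected at the time cannot be recovered.

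**Working it through.** **Step 1. The rules side by side.**

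| | Control | Experimental, module received | Experimental, module not received |
|---|---|---|---|
| T1 and T2 | collected | collected | collected |
| T3 trigger | contact one week after T2 | delivery of the module | none stated |
| T4 anchor | 7.2.4, but also named by the title of 7.2.3 | post-module assessment | none stated |

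The last column is the gap. No make-up visit, window or fallback appears in sections 3.3, 7 or 8.

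**Step 2. The plan's own figures (8.2).**

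- Parents as Teachers and SafeCare: d = .45, power .80, alpha .05, four assessments, 62 per group. The correlation over time is not stated for these trials, so I assume the .7 given for Incredible Years. For the between-group F test with f = .225, the noncentrality is 124 × .225² × 4 / (1 + 3 × .7) = 8.10. Power is 0.806 and 62 is the smallest size that reaches .80. A one-sided two-sample test also gives 62, so the method used cannot be identified.
- Incredible Years: 8.0025 × (1.960 + 0.842)² / (10 × 3 × .45²) = 10.34, rounded up to 11 groups. Recruiting 14 allows for 1 − 110/140 = 21% loss.

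Both sizes reproduce. Neither contains a rate of module non-receipt, and Parents as Teachers and SafeCare have no stated allowance for loss.

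**Step 3. Selection.** Let q be the share of experimental parents at T2 who do not receive the module. Let g be the amount, in SD, by which they would score below recipients without any module. Recipients then stand q × g above the mean of their arm before any effect. With an effect of .45 in recipients, all controls observed and no baseline adjustment, the observed contrast is .45 + q × g. The documents give neither q nor g; I assume q = 10%, 20%, 30% and g = 0.3.

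| q | Selection, q × g | Share of .45 | Observed contrast |
|---|---|---|---|
| 10% | 0.03 | 7% | .48 |
| 20% | 0.06 | 13% | .51 |
| 30% | 0.09 | 20% | .54 |

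For scale, one Incredible Years group of 10 that is not given the module is 10/140 = 7% of that arm.

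**Step 4. Offset from controls.** If a share c of controls misses T3 with the same gap g, the contrast is .45 + (q − c) × g. With q = 20% and c = 10%, selection falls to 0.03. With c above q, its sign reverses.

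**Step 5. Dilution, kept separate.** If non-recipients gain nothing, the effect of assignment is .45 × (1 − q) = .405, .36 or .315. That reduction is part of the effect of adding the module to a programme, so it is not a bias.

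**The case against.** The strongest reply is that the protocol is silent here and excludes no one. At T4 the research team contacts participants in general, by email or mail, and that text is not limited to recipients. This stands: the defect is a missing trigger and date. Leaving each site to improvise, however, gives no assurance that these parents are assessed, or assessed alike.

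Several stronger readings are tempting, and the documents do not support them.

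- **That such a parent is never assessed.** T1 and T2 exist and include the primary measure.
- **That any missed week loses T3.** A later delivery only moves T3. Section 2.3 describes SafeCare as about 18 weeks, of which T2 closes the first module, and 7.2.4 shows visits continuing in both home-visiting programmes.
- **That control T3 is secure.** It takes place at an ordinary session or, for Incredible Years, at an extra visit, and either can be missed. Section 14.0 provides dinner and childcare at the Incredible Years module session; none is stated for the control visit.
- **That the effect is overstated by 19%, 42% or 71%.** These are .48/.405, .51/.36 and .54/.315. They mix selection with dilution, and dilution makes up 60% of each gap (.045 of .075, .09 of .15, .135 of .225).

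It can also be said that a model using T1 and T2, with correlation .7, could remove much of a stable prognostic gap. That is fair, but 8.3 commits to no such model. Nor would adjustment recover the effect of assignment: in this arm receipt and observation coincide, so the data hold no T3 from an experimental parent without the module.

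**Conclusion.** The concern holds as a missing rule with a consequence for hypothesis (b). Experimental T3 depends on delivery, T4 depends on T3, and nothing covers a parent who stays in the programme without receiving the module. Followed as written, the between-arm comparison is open to selection after randomisation.

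The size and net direction are unknown. Selection of 0.03 to 0.09 SD, or 7% to 20% of .45, rests on an assumed 10% to 30% non-receipt, an assumed 0.3 SD gap, complete control data and no baseline adjustment. Missed control assessments would reduce it and could reverse it. A reader should not infer that the plan excludes these parents, or that an inflated effect is certain. The gap merits correction because the loss cannot be repaired afterwards and the means to prevent it are already in the protocol.

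**What to change.** - **7.2.4.** Set one T3 window counted from T2, the same in both arms. In the experimental arm, T3 is completed straight after the module if it is delivered within the window. Otherwise the research team obtains it at the end of the window by email or mail, as already done at T4, without the satisfaction and fidelity forms.
- **7.2.5.** Count T4 in both arms from T3, or from the end of the window if T3 is missed. Reconcile the control anchor, now given both as 7.2.4 and under the title of 7.2.3.
- **7.1 and 7.2.4.** Reconcile the timing of the module. The former places it at the end of the last session and the latter in the following week, and the window depends on which is meant.
- **8.3.** State that parents are analysed in the arm to which their site was randomised, whether or not the module was delivered. Record delivery (yes or no) and its date for each parent.

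The cost is a short amendment and a few extra contacts; the contact sheet, remote survey and T3 payment exist. A module delivered after the window would follow T3, and follow-up from module to T4 would then be shorter, which matters for hypothesis (a); the recorded date lets this be examined. The estimate will be somewhat smaller. Under the step 2 assumptions, Parents as Teachers and SafeCare power falls from 0.806 to 0.719 at 10% non-receipt and to 0.618 at 20%, where .80 would need 76 or 95 per arm.

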7.2.5 One-month Follow-up Assessment

Provide a description as defined above and format accordingly.

One month after 7.2.4, when intervention is complete -- the post-parenting intervention assessment for the control group and the post-module assessment for the experimental group, a member of the research team will follow up with participants using the preferred method of contact they indicated in 7.2.1 and distribute the final survey packet over email (link to an electronic version of the survey) or a hard copy through the mail with a prepaid envelope for return to Penn State. They will complete the Module Assessment and APQ.

7.3 Duration of Participation

Describe the duration of an individual subject's participation in the study.

Duration of participation for Incredible Years participants that is approximately 15 weeks (depending on mastery of the material), for Parents as Teachers participants that is approximately 6 weeks (depending on mastery of the material), and for SafeCare participants that is approximately 7 weeks (depending on mastery of the material). The control condition lasts the length of the parenting program in which they are participating (14 weeks for IY, depending on mastery of the material; 5 weeks for PAT, depending on mastery of the material; 6 weeks for SafeCare, depending on mastery of the material). The one week of

follow up is outside the provision of the program. Total participation extends one month beyond that to include the final follow-up assessment.

The estimated total time for a participant in the experimental condition to complete all assessments is 60 minutes; the estimated total time for a participant in the control condition to complete all assessments is 55 minutes.

Providers participation in fidelity research (i.e., self-report will be approximately 5 minutes in all sessions they deliver the SPSHK module.

8.0 Subject Numbers and Statistical Plan

8.1 Number of Subjects

Indicate the total number of subjects to be accrued.

If applicable, distinguish between the number of subjects who are expected to be enrolled and screened, and the number of subjects needed to complete the research procedures (i.e., numbers of subjects excluding screen failures.)

The number of subjects needed for the PAT randomized controlled trial is 124: 62 randomized to the control group, 62 randomized to the experimental group.

The number of subjects needed for the SafeCare randomized controlled trial is 124: 62 randomized to the control group, 62 randomized to the experimental group.

The number of subjects needed for the Incredible Years cluster randomized controlled trial is 280: 140 randomized to the control group, 140 randomized to the experimental group.

We expect to enroll approximately 100 provider-subjects for the fidelity research.

In total we expect to enroll 628 subjects, both parent and provider-subjects.

8.2 Sample size determination

If applicable, provide a justification of the sample size outlined in section 8.1 – to include reflections on, or calculations of, the power of the study.

Parents as Teachers and SafeCare

In a two-arm RCT, sample size is determined by power and estimated effect size. We are doing a repeated measures design (4 assessments), so this must be accounted for in the sample size calculation. Assuming a desired power of .8 and estimated effect of .45, the sample size needed to detect an effect at alpha .05 is 62 individuals per group ($N = 124$) for each trial. That is, 124 participants for Parents as Teachers and 124 participants for SafeCare.

Incredible Years

Because the additive approach of our research is novel, we are relying on prior CSA prevention and general PE program research to estimate the effect size. A meta-analysis of general PE programs, from which CSA programs were excluded, found the estimated average effect size for trials including a control group to be $d = .3$. A meta-analysis of CSA-specific prevention programs (Davis & Gidycz, 2000) reported the average effect size for a single session program to be $d = .59$. Averaging these findings, we estimate the effect size of our module to be $d = .45$. The group-based delivery of IY requires the experimental design to be a cluster RCT and, as such, clustering must be considered in sample size calculation (i.e.,

participants are nested within groups). In order to calculate the required sample size for the cluster randomized trials, we used the sample size calculation equation (Equation 1) for repeated measures from Heo and colleagues (2009; Equation 19, p. 385). Cluster sampling introduces a less precise estimate of parameters than simple random sampling (e.g., commonalities among participants); this increase of variance is estimated in the design effect ($2f$). Our design has repeated measures, which introduces autocorrelation (C_f); for our purposes we estimate this to be .7. Together, the design effect and the autocorrelation of the outcome of interest over time creates the corrected design effect ($2fC_f$), estimated to be 8.0025 for our calculation. Assuming $\alpha = .05$, $\beta = .80$, 10 participants per group (N_2), 3 measurement occasions (N_1), and an effect size (Δ) of 0.45, the number of groups needed per condition (N_3) is 11; this is in agreement with simulated sample sizes presented by Heo et al. (2009; Table 1). To account for participant attrition and lack of participation in research, **we will recruit 14 groups per condition such that our sample is comprised of ~ 280 participants (140 per condition).**

Equation 1.

$$N_3 = \frac{2fC_f(\phi^{-1}(1 - \frac{\alpha}{2}) + \phi^{-1}(1 - \beta))^2}{N_2N_1\Delta^2}$$

Fidelity

Other research indicates that two audio recorded sessions from 100 provider-subjects will be sufficient to answer fidelity research questions.

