4.0 Recruitment Methods

4.1 Identification of subjects

Describe the methods that will be used to identify potential subjects or the source of the subjects. If not recruiting subjects directly (e.g., database query for eligible records or samples) state what will be queried, how and by whom.

StudyFinder: If you intend to use StudyFinder (<http://studyfinder.psu.edu>) for recruitment purposes, please indicate this in section 4.1 along with any other methods for identifying subjects. Note that information provided in this protocol should be consistent with information provided on the StudyFinder page in your CATS IRB study.

For Penn State Hershey submissions using Enterprise Information Management (EIM) for recruitment, attach your EIM Design Specification form on the Basic Information page in CATS IRB (<http://irb.psu.edu>). See HRP-103 Investigator Manual, "What is appropriate for study recruitment?" for additional information.

We will utilize our relationship with community partners (i.e., providers of the parent-education programs) and Children and Youth agencies to recruit provider agencies.

After obtaining provider buy-in at both experimental and control sites, we will recruit participants directly through providers at these agencies.

For experimental sites, that is those who are randomized to add the CSA module onto the existing PE program, providers will be recruited to participate in the fidelity research at the time of training in SPSHK.

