7.0 Study Design and Procedures

7.1 Study Design

Describe and explain the study design.

This research will utilize a randomized controlled trial (RCT) design. As this research includes three parenting programs, Incredible Years, PAT, and SafeCare, three RCTs will be conducted simultaneously. Randomization will occur at the site level to reduce the potential for contamination; as such, recruited parents will not be informed of the randomization process. When sites agree to participate (i.e., be randomized) they agree to implement the evidence-based parenting program plus the added module as they would typically implement the parenting program. Although the module is not evidence-based, they are agreeing to deliver as if it were standard procedure.

This section describes the design and procedures for the three RCTs: (1) *Incredible Years RCT*; (2) *Parents as Teachers RCT* and (3) *SafeCare RCT*. However, there are commonalities between the three trials:

- There will be two groups of providers— one assigned to deliver the parenting program and one assigned to deliver the parenting program plus additional SPSHK module at the end of the last session (described below), in support of the research question.
- Parents in the control group will complete assessments at four time points: pre-parenting intervention, post-parenting intervention, one-week post parenting, and one month post-intervention.
- Parents in the experimental group will complete assessments at four time points: pre-parenting intervention, post-parenting intervention, post-module, and one month post-intervention.
- For the experimental group, fidelity monitoring procedures will also occur in sessions for each enrolled provider-subjects. Parents and provider-subjects of these sessions will each complete a fidelity assessment instrument. With the parent’s permission, the provider will audio record two experimental sessions.

Different measures will be asked at specific assessment periods:

Measure Name (file name in supporting documents attachments)	Construct	Timing of Delivery (by Protocol Section description paragraph)
Alabama Parenting Questionnaire (APQ; ‘Measure_APQ.docx’)	Parenting behaviors and responding to child’s externalizing behaviors: subscales of Parental Involvement, Positive Parenting, Inconsistent Discipline Practices	7.2.1, 7.2.3, 7.2.5, 7.2.6

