17.0 Other Approvals

17.1 Other Approvals from External Entities

Describe any approvals that will be obtained prior to commencing the research (e.g., from cooperating institutions, community leaders, schools, external sites, funding agencies).

Agencies that implement Incredible Years or PAT or SafeCare parent-training programs will be approached by mail, email, and/or phone call and invited to participate in the study. Presentations or webinars will be made available to provide more information should agencies desire. Facilitators (i.e., the individuals who actually implement the programs with parents) will then be recruited and then randomized to either (a) business-as-usual implementation of their respective program or (b) implementation of their respective program and the additional, one-session CSA module. As we recruit sites to participate we will ask about their required approvals. At this time, no site that has agreed to participate has an external approval process. All they require is a letter from the PSU IRB saying this research is approved.

As a site is recruited, a document agreement will be acquired from someone in an oversight position who has a decision-making capacity over potential subjects.

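### PAT and SafeCare are randomised by site (or facilitator) but sized as 62 independent parents per arm with no attrition allowance, so the stated 80% power is not justified for that design

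*Combined protocol and SAP*

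**What the plan says.** Section 7.1 introduces three simultaneous RCTs and gives one allocation rule for all of them: "Randomization will occur at the site level to reduce the potential for contamination". Section 4.1 agrees: "For experimental sites, that is those who are randomized to add the CSA module onto the existing PE program". Section 17.1 names a different unit. After agencies are approached, it is the facilitators who "will then be recruited and then randomized to either (a) business-as-usual implementation of their respective program" or to the program plus the module. No section describes a procedure for allocating individual parents.

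For PAT and SafeCare, section 8.2 starts from power .8, an effect of .45 and four assessments, and concludes that "the sample size needed to detect an effect at alpha .05 is 62 individuals per group". It gives no ICC, number of units, parents per unit, design effect or attrition term.

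Incredible Years is treated differently in the same section. Clustering enters because "The group-based delivery of IY requires the experimental design to be a cluster RCT", and 11 groups per condition become 14: "To account for participant attrition and lack of participation in research".

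Section 8.1 repeats 124 for each of the two trials and closes with "In total we expect to enroll 628 subjects, both parent and provider-subjects". Section 8.3 lets the model depend on recruitment and participating sites, treats control for nesting as a possibility, lists simple t-tests among the options, and says the study is powered for a between-factor repeated-measures ANOVA.

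**The concern.** When whole sites or facilitators are allocated, parents in the same unit share an agency or provider, and their scores may be correlated. The variance of the arm difference then exceeds that for independent parents, and a sample size that ignores this overstates power. Home visiting removes the shared group session that section 8.2 cites for Incredible Years. It does not remove the shared randomised site or provider.

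Two things are at stake. First, section 1.2 defines the primary endpoint as reaching enough parents to be powered and points to section 8, so two of the three trials rest on a calculation made for a different design. Second, section 8.3 permits analyses that ignore the unit, and these would raise the false-positive rate whatever the power is.

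Attrition is a lesser part of the same gap. Sections 3.3.2 and 9.1.1 foresee withdrawal and loss to follow-up, but the PAT and SafeCare numbers carry no margin for either.

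**Working it through.** **Inputs from the documents.** Alpha .05, power .80, d = .45, m = 4 assessments and n = 62 per arm (8.1, 8.2); between-factor repeated-measures ANOVA (8.3). A correlation between assessments of rho = .7 is stated for Incredible Years only and is borrowed here. Sidedness is not stated for PAT and SafeCare. Two-sided is assumed, because Equation 1 for Incredible Years uses alpha/2.

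**Reproducing 62.** The variance factor for the mean of four assessments is (1 + 3 × .7)/4 = .775. The noncentrality is λ = n d²/(2 × .775).
- n = 62: λ = 62 × .2025/1.55 = 8.10, power .806.
- n = 61: power .7997.

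So 62 is the smallest n that reaches 80% for independent parents with complete data. A one-sided t-test on a single assessment also gives 62 (power .801), again for independent parents. A two-sided t-test on a single assessment needs 79.

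**Is 124 a completer count?** No: 124 + 124 + 280 + 100 = 628, the number section 8.1 expects to enrol.

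**Adding the randomised unit.** ICC and parents per unit (k) are not in the documents, so every value below is an assumption. Two design effects (DE) bracket how far unit effects persist across the four assessments:
- usual: DE = 1 + (k − 1) ICC;
- fully persistent: DE = (1 + 3rho + 4(k − 1) ICC)/(1 + 3rho).

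Power uses λ = 8.10/DE, with complete data:

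| ICC | k | DE, usual / persistent | Power, usual / persistent |
|---|---|---|---|
| .01 | 5 | 1.04 / 1.052 | .791 / .786 |
| .02 | 10 | 1.18 / 1.232 | .739 / .720 |
| .05 | 10 | 1.45 / 1.581 | .650 / .613 |

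**Few sites.** The table keeps parent-level degrees of freedom. A site-level t-test with 2S − 2 degrees of freedom, where S is the number of sites per arm, gives about .76 (S = 12, ICC .01), .64-.65 (S = 6, ICC .02) and .53-.56 (S = 6, ICC .05).

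**Dropout alone.** If lost parents contribute no data, 10% loss (n = 55.8) gives .763 and 20% loss (n = 49.6) gives .712. If each lost parent still contributes one to three analysed surveys, power is .797-.805 at 10% loss and .788-.804 at 20%.

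**Ignoring the unit in the analysis.** The two-sided false-positive rate is 2[1 − Φ(1.96/√DE)]. With k = 10 it is .071-.077 at ICC .02 and .104-.119 at ICC .05.

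**The case against.** The strongest reply is that the illustrated losses belong to one test under one correlation. That stands. With rho = .5, independent-parent power is .882, and the three cases in the table become .862-.869, .791-.825 and .669-.743. The regression models in section 8.3 would also allow the first post-module score to be adjusted for baseline. At rho = .7 the variance factor is then 1 − .49 = .51, and power is about 94% unclustered. It is 93%, 89% and 82% in the same three cases, using the usual design effect and taking the ICC to apply to the adjusted outcome. The averaged test also assumes d = .45 at all four assessments, although the first two precede the module. A reader might infer from the table that PAT and SafeCare have some particular power below 80%, or that any modest clustering or dropout must take them below it. The documents support neither.

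A second reply is that section 17.1 is an approvals section, so its facilitators may simply be assigned through their sites. That is possible, and it would make the conflict one of wording. Parents would still be nested.

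A reader might also infer that randomising facilitators leaves very few parents per unit and so rescues the 80%, on the strength of "We expect to enroll approximately 100 provider-subjects for the fidelity research". That count does not map onto trial parents. Section 8.2 expects two recordings from each of 100 providers, or 200 sessions, while the experimental arms imply about 62 + 62 + 14 = 138 module deliveries. Parents per facilitator cannot be derived from it.

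Section 8.1 does speak of 62 randomised to each group, which might suggest individual allocation. It gives counts only, and sections 7.1, 4.1 and 17.1 all name a higher unit.

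Finally, dropout costs little if partial data are analysed, and section 3.3.2 keeps available surveys when the parent agrees. Attrition is therefore secondary to clustering.

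**Conclusion.** The point holds as a mismatch between design and calculation. The arithmetic behind 62 is right for independent parents with complete data, but that is not the design in section 7.1 or section 17.1. The 80% power for PAT and SafeCare is therefore not justified as written.

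How far true power lies from 80% cannot be settled, because ICC, units per arm, parents per unit and dropout are absent and rho is borrowed. The table's range of about 61% to 79% illustrates the named test only. Power would be lower with few sites, and higher with a smaller rho or a baseline-adjusted post-module analysis. Dropout matters mainly if partial data are not analysed.

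The validity risk is separate from power. An analysis that ignores the unit, which section 8.3 leaves open, would have a two-sided false-positive rate of about 7-8% (ICC .02) or 10-12% (ICC .05) at 10 parents per unit, again under assumed values. This should be corrected before the analysis is fixed.

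**What to change.** 1. Reconcile sections 7.1 and 17.1 on one unit of randomisation.
2. In section 8.2, recalculate PAT and SafeCare for the chosen primary analysis, with a design effect for that unit and an expected dropout rate. State the ICC, units per arm, parents per unit, rho and sidedness. Restate the power or detectable effect at 62 per arm as a range.
3. In section 8.3, replace the optional wording on nesting with a commitment that each trial's primary analysis accounts for the randomised unit and uses all available assessments. One example is a mixed model with a random effect for that unit and small-sample degrees of freedom.

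The cost is some rewording, one recalculation and one sentence in section 8.3. The fix itself does not call for more enrolment or any change to procedures. The downside is that the stated power may be less favourable, and restating it does not restore any power that is lacking.
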